### 11.3 Data Analysis Plan:

**Primary Analysis:** *(Hypothesis 1) Subjects with PTSD randomized to acute therapy with Riluzole will have a superior response rate acutely compared to subjects randomized to placebo.*

The PI will be primarily responsible for data analysis in this study. He will be assisted by a data analyst or analysts within the Department of Psychiatry at USUHS and this person (or persons) will be added to the protocol as investigators (with IRB approval) prior to any handling of the data. The primary intent of this study is to compare the efficacy of riluzole relative to placebo in the treatment of overall anxiety symptomatology of subjects who have PTSD. This will be analyzed by comparing reductions from baseline scores on the CAPS total score after up to 8-weeks of double-blind therapy to the original score before the start of therapy using t-tests or Mann-Whitney U tests when assumptions for t-tests are not satisfied.

In addition to utilizing the CAPS continuous score, scores will also be dichotomized to examine clinical responders versus non-responders in the treatment and placebo groups. A responder will be defined as any patient who demonstrates a 30% or greater decrease in CAPS total score from baseline (phase I) to the last measured value of Phase II. Response rate analyses will then be performed by comparing the proportion of subjects in each treatment group who met the response criteria. Response rates will be analyzed using Pearson's chi-square test or Fisher's exact test when expected cell sizes are less than 5.

In order to more thoroughly assess the effects of treatment status in a longitudinal setting, random effects regression will also be used to examine the study groups over time in the presence of additional covariates.

In general, variables that are continuous, yet non-normally distributed, will be appropriately transformed or will be analyzed using appropriate non-parametric tests. Variables that are non-continuous (ordinal, nominal) will be analyzed using appropriate non-parametric tests. All tests of hypotheses will be tested at a two-sided a level of 0.05.

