#### 9.4 Objectives/Specific Aims/Research Questions:

Describe the purpose and objective(s) of the study, specific aims, and/or research questions/hypotheses

**Objective:** To evaluate the efficacy of acute riluzole treatment (100-200mg/day) in 158 active duty and returning OIF, OEF, and OND veterans, aged 18 to 65 with a diagnosis of PTSD, with or without mTBI, who are sub-optimally responsive to their current medication treatment (8 weeks).

**Hypothesis 1:** *Subjects with PTSD, with or without mTBI, who are only partially responsive to initial therapy (e.g., CAPS score greater than or = 40 at the completion of an adequate trial of medication therapy) who are subsequently randomized to augmentation therapy with riluzole will have a superior response rate compared to subjects randomized to placebo.*

**Hypothesis 2:** *PTSD patients randomized to augmentation with riluzole therapy will have significant improvement in depression, anxiety and global functioning compared to those who receive placebo in addition to their pre-study PTSD medication.*

**Hypothesis 3:** *The N-acetyl aspartate to creatine ratio (NAA/Cr) in the hippocampus and anterior cingulate, measured using magnetic resonance spectroscopy (H MRS), will increase after 8-week treatment with riluzole.*

In addition to indicating simple change in severity, the change in CAPS total score will be the primary outcome variable at the end of Phase II (Visit 10). We believe this study is powered to detect a 9 point or greater difference in CAPS total score from baseline between riluzole and placebo augmentation (after Phase I) to the last measured value of Phase II.

The following scales are proposed for primary and secondary outcome measures:

- i. Primary Outcomes Assessment:** Clinician-Administered PTSD Scale (CAPS), Clinical Global Impression of Severity (CGI-Severity), Clinical Global Impression of Improvement (CGI-Improvement).
- ii. Secondary Outcomes Assessment:** Montgomery-Asberg Depression Rating Scale (MADRS), Hamilton Anxiety Rating Scale (HAM-A), Sheehan Disability Scale (SDS), PTSD Checklist (PLC-C), UKU Side Effect Rating Scale, Self-rating version.
- iii. Additional secondary outcome measure:** Changes in NAA levels in the hippocampus and anterior cingulate cortex following riluzole or placebo administration measured using H MRS.

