### a. Method of Collection from Study Participants.

**Primary Outcomes Assessment** – All study assessment materials are in the public domain and will not be altered. Each measure includes a minimum of one citation attesting to the reliability and validity of

the questionnaire based on the consensus of researchers published in the field of behavioral science. In general, each measure has a minimum assessment level of 'adequate', with the majority assessed at a level of 'good' or higher.

Instruments selected are well established neuropsychological questionnaires with extensive clinical and research validation and are structured to ensure the highest levels of clarity and ease of administration. Participants will have no difficulty in reliably completing these instruments in a clinical setting. This instrument battery is currently in use in several WRNMMC-approved research projects conducted by the Investigator in both the inpatient ward and outpatient clinics at WRNMMC. Further, this instrument battery is in use by the INTRuST Clinical Consortium, which is a multi-site research collaboration on PTSD and TBI, which will allow de-identified data from this study to be compared across a nationally-representative dataset. Assessments not directly related to the primary outcome are being made to allow for comparability with these other ongoing trials in this population, and all questionnaires were selected and rigorously reviewed to ensure that content overlap was minimized in the interest of participant welfare. As such, no unnecessary measures are included, and all data collected will be analyzed and results reported and disseminated.

**1. Clinician-Administered PTSD Scale (CAPS):** The CAPS (Blake et al 1995; Blake et al., 1990) is a lengthy structured interview based on the DSM-IV that assesses the presence and severity of PTSD and associated symptoms. Changes from baseline to endpoint in the CAPS total score will serve as the primary efficacy measure for the double blind phase. The CAPS is widely accepted as the Gold Standard for establishing PTSD diagnosis with excellent reliability and validity (Blake et al., 1990; 1995), (Weathers et al., 1999).

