**11.0 Statistical/Data Analysis Plan**

**11.1 Statistical Considerations:**

List the statistical methods to be used to address the primary and secondary objectives, specific aims, and/or research hypotheses. Explain how missing data and outliers will be handled in the analysis. The analysis plan should be consistent with the study objectives. Include any sub-group analyses (e.g., gender or age group). Specify statistical methods and variables for each analysis. Describe how confounding variables will be controlled in the data analysis

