### 5.7.1 Data Analysis Table

Independent Variable / Predictor	Dependent Variable/ Outcome	Statistical Test
Riluzole/placebo	PTSD anxiety symptomatology (CAPS total score)	t-test/Mann-Whitney U test
Riluzole/placebo	Clinical Response Rate	Pearson's chi-square test, Fisher's exact test
Riluzole/placebo	Effects of treatment status longitudinally	Regression Analysis
Riluzole/placebo	Origin, gender, age, dose level, illness characteristics	ANOVA, Mantel-Haenszel common odds ratio test, Breslow-Day test
Riluzole/placebo	NAA/Cr ratio	t-test/Mann-Whitney U test
Not Applicable	Not Applicable	Descriptive Statistics

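### The lead CAPS test ignores baseline CAPS and takes early leavers at their exit value, with no stated estimand or sensitivity analysis for early exit

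*Combined protocol and SAP*

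**What the plan says.** Section 11.3 (Primary Analysis) ties the main intent of the study to reductions in the "CAPS total score after up to 8-weeks of double-blind therapy", compared with the score before therapy "using t-tests or Mann-Whitney U tests when assumptions for t-tests are not satisfied". The Data Analysis Table (5.7.1) lists the same two tests. Neither place names a covariate.

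Section 10.2 makes CAPS change the primary measure: "Changes from baseline to endpoint in the CAPS total score will serve as the primary efficacy measure for the double blind phase". Section 9.4 words the change as running "after Phase I) to the last measured value of Phase II". The footnote to the schedule of events puts the exit visit at Visit 9, or sooner if the participant is discontinued.

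Section 11.3 adds that "random effects regression will also be used to examine the study groups over time in the presence of additional covariates". The table lists this as "Effects of treatment status longitudinally", tested by regression analysis. The covariates and the contrast are not named.

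The form's own prompt in Section 11.1 reads "Explain how missing data and outliers will be handled in the analysis". Sections 11.1 to 11.3 give no explicit answer: there is no missing-data method, analysis set, estimand or sensitivity analysis.

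The schedule shows CAPS at Screening, Visit 1 (week 0), week 5 and week 8. Section 9.4 calls the end of Phase II Visit 10; the schedule and the Acute Trial Assessments text call it Visit 9.

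**The concern.** There are two separate matters.

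The first is efficiency. CAPS before treatment is measured in everyone and is likely to be related to CAPS at week 8. A test on raw change uses that information in a fixed way, whereas a linear model with baseline CAPS as a covariate uses it optimally. Two pre-treatment CAPS values exist, so which of them is baseline should be stated.

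The second is early exit. Using the last measured value is in effect a carry-forward rule, although the plan does not call it that. Section 9.5 (Phase II) and Section 14.2 take participants out for intolerance, worsening or raised liver tests. These reasons could be commoner in either arm. If improvement accumulates over 8 weeks, a participant assessed at week 3 contributes less improvement than one assessed at week 8. The arm with more exits then looks worse for that reason alone. Whether this is bias depends on what the trial means to estimate, and the plan does not say.

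**Working it through.** **1. The plan's own figure.** Inputs from Section 11.2: 50 per arm, difference 9, SD 15, two-sided 0.05. The standard error is 15 × √(2/50) = 3.0, so the noncentrality is 9/3 = 3.0 on 98 degrees of freedom. Noncentral-t power is 0.844, as stated.

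**2. Gain from baseline adjustment.** The plan does not say whether 15 is the SD of the score or of the change; I take it as the SD of change. Let r be the correlation between baseline and week-8 CAPS and k the ratio of baseline SD to week-8 SD. Both are assumed.

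- Week-8 SD = 15/√(1 + k² − 2rk)
- ANCOVA residual SD = week-8 SD × √(1 − r²)
- Example, k = 1 and r = 0.5: week-8 SD 15.0, residual SD 15 × √0.75 = 12.99

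Power with 50 per arm and difference 9:

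| k | r = 0.3 | r = 0.5 | r = 0.7 |
|---|---|---|---|
| 1.0 | 0.958 | 0.929 | 0.896 |
| 0.8 | 0.918 | 0.882 | 0.851 |
| 0.7 | 0.896 | 0.862 | 0.844 |

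At k = 0.7 and r = 0.7 the residual SD is 15.0 and nothing is gained. A ratio below 1 is plausible because entry requires CAPS of at least 40, which may narrow the baseline spread.

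**3. Last value against the target of week 8 had all continued.** Illustrative assumptions, none of them in the documents: improvement is linear in time, placebo improves 12 points by week 8, and exit weeks are uniform over 1 to 7. The mean exit week is then 4, so a leaver carries half the 8-week gain, and an arm with gain G and exit rate p has a mean last-value change of G(1 − p/2).

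Exit rates of 32% and 43% are the non-completion rates in the two small open-label depression studies in Section 14.1 (68% and 57% completed). The paired lower rates of 15% and 20% are my own.

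No drug effect (G = 12 in both arms): the difference is 12 × (pP − pR)/2, where pR and pP are the riluzole and placebo exit rates.

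- Equal exits: 0
- 32% and 15%: 12 × 0.17/2 = 1.02 points against the arm with more exits
- 43% and 20%: 12 × 0.23/2 = 1.38 points against the arm with more exits
- If placebo improves 6 or 18 points instead, the range widens to 0.5 to 2.1 points

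With SD 15, shifts of 1.02 and 1.38 give rejection rates of 0.063 and 0.074. Simulation of the last-value t-test (20,000 trials per scenario) gives 0.06 to 0.08.

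True 9-point effect (G = 21 and 12): the difference is 21(1 − pR/2) − 12(1 − pP/2).

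- 32% in both arms: 17.64 − 10.08 = 7.56
- 32% riluzole, 15% placebo: 17.64 − 11.10 = 6.54
- 15% riluzole, 32% placebo: 19.425 − 10.08 = 9.35

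The last value can therefore fall below or above 9.

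**4. The same rule against other targets.** Suppose leavers in both arms stay at their exit level. With no drug effect at 32% and 15%, the true week-8 means regardless of stopping are 10.08 and 11.10, a difference of 1.02. The last-value difference is the same 1.02, so its bias for that target is zero. If the target is outcome while on treatment, the last value is itself the measurement.

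**The case against.** The strongest reply is that the plan may intend outcome while on treatment. Section 11.3 speaks of therapy lasting up to 8 weeks, and an exit assessment is scheduled for leavers. On that reading the last value is the right quantity. This stands. A reader might infer that the last-value rule is biased whatever the estimand; step 4 shows that it is not. The remaining complaint is that the estimand has to be deduced.

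A reader might also infer that the plan leaves open which analysis leads. The text does not support that. Section 11.3 attaches the primary intent to the t-test comparison and says the regression will also be used, which reads as supplementary. The fair complaint is that the regression's covariates and contrast are unnamed and that it is given no role in handling early exit.

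Nor do the differing baseline and endpoint phrases all conflict. The Week 8 or Visit 9 wording, and the phrase "from baseline (phase I) to the last measured value of Phase II", define the responder outcome. The t-test sentence has its own baseline, the score before therapy. What is left is Visit 10 against Visit 9, and Screening against Visit 1.

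The sizes in step 3 rest on assumed exit rates and trajectories. The two open-label studies had no placebo arm, so unequal exit is a possibility and not a forecast. A bias of 1.0 to 1.4 points is also less than half the 3-point standard error.

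Finally, withdrawal and data monitoring refer to a legacy protocol that was not supplied. Section 11 makes no such reference, so this tempers confidence without changing the reading.

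**Conclusion.** The point holds in a limited form. The lead test leaves out a covariate that is already collected, and the plan takes early leavers at their exit value without naming an estimand or testing the result's sensitivity to early exit.

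The t-test is valid with complete data, and the power of 0.844 is right for it. Baseline adjustment would take power to between 0.844 and 0.958 over the assumed correlations and SD ratios; it lost nothing in any case checked, and in one it gained nothing. The early-exit bias applies only if the target is week 8 had all continued, improvement builds over time and, under no drug effect, exit rates differ between arms. It is then 1.0 to 1.4 points under the central assumptions, in an unknown direction.

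A reader might infer that a mixed model must become the primary analysis. That follows only if the had-all-continued estimand is chosen. This should be corrected before analysis, but it does not invalidate the design.

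**What to change.** - State the estimand for the CAPS comparison in Section 11.3.
- Replace the unadjusted t-test with ANCOVA (a linear model) on baseline CAPS, with site as a covariate, in all randomised participants with a post-baseline CAPS. Say whether Screening or Visit 1 is baseline. The unadjusted test can stay as a supporting analysis.
- Make the random-effects regression a named sensitivity analysis for early exit, or the primary analysis if the had-all-continued estimand is chosen. Enter each exit CAPS at its actual week, take the week-8 treatment difference as the contrast, and list the covariates. CAPS is planned only at weeks 5 and 8 after Visit 1, so the form of the time effect should be written down in advance.
- State the missing-at-random assumption and add one analysis that departs from it, for example with leavers worse than predicted by a stated number of points, varied by arm.
- Correct Visit 10 in Section 9.4 against Visit 9 in the schedule and the Acute Trial Assessments text.

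The cost is protocol and analysis-plan wording and slightly more analysis work. No visit or assessment is added.

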**Abbreviations:** Sc = Screening Visit; Sta = Stabilization Visit; CAPS = Clinician-Administered PTSD scale; CD-RISC = Connor-Davidson Resilience Scale; CGI = clinical global impression scale; CTQ = Childhood Trauma Questionnaire; DES = Dissociative Experience Scale; F/U = Follow-up visit; HAM-A = Hamilton Anxiety Rating Scale; HCG = blood pregnancy test; Hollingshead = Hollingshead 4 Factors of Social Status Scale; LSAS = Liebowitz Social Anxiety Scale; MADRS = Montgomery Depression Rating Scale;; PLC-C = PTSD Checklist; UKU-SERS-Pat = UKU Side Effect Rating Scale, Self rating version; PDI = Peri Traumatic Distress Inventory; PSQI = Pittsburgh Sleep Quality Index; SCID-IV-TR = Structure Clinical Interview for DSM-IV; SCR = screen; SCL-90 = Symptom Checklist, 90 items; SDS = Sheehan Disability Scale; WHOQOL BREF = World Health Organization Quality of Life WO = washout phase.

aExit visit to be performed at Visit 9 or sooner if the patient is discontinued from the study.

WO = washout phase. May vary depending on drug but in general is 51/2 lives. If the subject is medication free, they may proceed to Study Period I.

bVisits during Study Period II may happen within 2 days of the scheduled visit. SCO = Standard of Care activity - Affirmative notation; Default notation is left blank indicating an activity that is research-related.

The 10-week clinical study will be conducted in two phases, a minimum of 2-weeks and maximum of 4-weeks screening and stabilization phase (Phase I) and an 8-week double-blind placebo controlled treatment (Phase II).

In Phase I, indicated as the "Screening Period" in **Figure 1 Riluzole Augmentation for PTSD**, patients who are suboptimal responders (see inclusion/exclusion criteria) to other psychotropic drugs will continue these at stable dosage for at least 2 weeks prior to study randomization (dose stabilization). Use of antidepressant and sedative/hypnotic drugs at stable dose is permitted. Subjects will be contacted by phone after 1 week to assure that no medication changes were made and to schedule the first Phase II visit.

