Subjects will also complete the screening visit where they will be evaluated for study entry and enrollment. Psychiatric history and diagnosis will be administered by study staff at each site using the SCID-P (First et al., 1995) and the DSM-IV Diagnostic Criteria (American Psychiatric Association, 1994). Patients who meet DSM-IV criteria for PTSD must have a Clinician Administered PTSD Scale (CAPS) of 40 at Visits 1 and 2 to be included in the study. Those entering the study at the completion of a referring INTRuST or other medication trial for PTSD will also receive a CGI assessment, and must have a score indicating "NOT improved" or "NOT very much improved" on the CGI scale at the completion of their medication trial to be eligible. The screening visit will include the screening tests, patient history, and psychiatric and physical examinations, as well as menstrual history in females. Subjects will undergo a physical exam, supine and standing vital signs, complete blood cell counts (CBC) with differential, electrolytes, thyroid function test, liver function tests, fasting blood sugar, hematology profile, urinalysis (including screens for substances of abuse), hepatitis screen, SCID, and CAPS. Women of childbearing capacity will have a baseline serum  $\beta$ -HCG. A positive  $\beta$ -HCG will exclude them from participating in the study. Subjects must also have a negative Human Immunodeficiency Virus (HIV) test. Results of these tests will identify patients who should be excluded because of active medical problems or substance abuse that might affect the clinical phenomenology or treatment response and to identify conditions that might make randomization into one of the treatment arms less safe. The CGI will be used to collect information on overall improvement, and the UKU side effect rating scale will be used to collect information on side effects. Finally, eligible subjects who consent to participate in the baseline  $^1\text{H}$  MRS portion of the study will undergo the scan during the screening visit.

The time commitment for the telephone confirmation is estimated to be 10 minutes. The screening visit will take 4 hours. The time commitment for the baseline  $^1\text{H}$  MRS scan is estimated to be 60-90 minutes.

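### Free improvement, not an error: the primary CAPS test is a valid but unadjusted comparison of change scores; ANCOVA on the week-0 CAPS already scheduled would usually be more precise

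*Combined protocol and SAP*

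**What the plan says.** **Primary test.** Section 11.3 compares reductions in CAPS total score between riluzole and placebo "using t-tests or Mann-Whitney U tests when assumptions for t-tests are not satisfied", at a two-sided 0.05 level. Table 5.7.1 assigns the same pair of tests to the row "PTSD anxiety symptomatology (CAPS total score"). Section 11.2 powers an unadjusted two-sample t-test: difference 9, SD 15, 50 per group, power 0.844.

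**Where covariates appear.** Section 11.3 adds that "random effects regression will also be used to examine the study groups over time in the presence of additional covariates". This model is supplementary and its covariates are not named. The ANOVA models in 11.3 serve subgroup analyses, which are declared secondary.

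**What is measured.** The schedule in section 9.5 marks CAPS at screening, V1 (week 0), V6 (week 5) and V9 (week 8). MADRS, HAM-A, SDS and PCL-C are also marked at V1.

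**Which value is baseline.** Section 11.3 refers to the score before therapy starts, which fits both screening and week 0. Its responder rule runs "from baseline (phase I) to the last measured value of Phase II". Section 9.4 instead places the starting point after Phase I: "riluzole and placebo augmentation (after Phase I) to the last measured value of Phase II".

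**The concern.** A t-test on change implicitly assumes that a patient one point higher at baseline ends, on average, one point higher at endpoint. When the true slope is below 1, subtracting the whole baseline adds noise that a fitted slope would remove. A chance difference in baseline CAPS between arms also passes partly into the estimated effect. That averages to zero over randomisations, but it can matter in the one trial that is run.

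What is at stake is precision for a 9-point target, in a trial whose only stated sample-size allowances are for ineligibility and for the balance of recruitment between sites. The covariate is a value the change score already needs, so the same patients and the same endpoint are analysed. The covariate must be a single defined value, however, and the plan's wording does not settle which one.

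**Working it through.** **Inputs from the documents.** Difference 9, SD 15, 50 per group (11.2); two-sided alpha 0.05 (11.3); 1:1 allocation (9.5).

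**Inputs assumed.** Baseline-endpoint correlation r from 0.3 to 0.8, and k = baseline SD / endpoint SD. Section 11.2 does not say what the SD of 15 describes. Section 9.4 speaks of power for a difference in CAPS from baseline, so 15 is first taken as the SD of change. All figures concern the t-test branch.

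**1. The plan's own figure.** SE = 15 × √(2/50) = 3.00; noncentrality 9/3.00 = 3.0; 98 df. Exact power is 0.8439, against the stated 0.844.

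**2. Why ANCOVA is not less precise in large samples.** With endpoint SD s and baseline SD ks:
- variance of change = s²(1 + k² − 2kr)
- ANCOVA residual variance = s²(1 − r²)
- difference between them = s²(k − r)², which is never negative.

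With equal SDs (k = 1), the ratio of ANCOVA variance to change variance is (1 + r)/2.

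**3. SD of change = 15, k = 1.** ANCOVA SD = 15 × √((1 + r)/2). Power uses 97 df and multiplies the variance by 1 + 1/(2n − 4) = 1 + 1/96, the price of estimating the slope.

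| r | ANCOVA SD | SE | 95% CI half-width | Power |
|---|---|---|---|---|
| unadjusted | 15.00 | 3.00 | 6.0 | 0.844 |
| 0.3 | 12.09 | 2.43 | 4.8 | 0.956 |
| 0.5 | 12.99 | 2.61 | 5.2 | 0.927 |
| 0.7 | 13.83 | 2.78 | 5.5 | 0.893 |
| 0.8 | 14.23 | 2.86 | 5.7 | 0.876 |

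**4. If 15 is the SD of a single score, k = 1.** SD of change = 15 × √(2(1 − r)); ANCOVA SD = 15 × √(1 − r²).

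| r | SD of change | Power, t-test | ANCOVA SD | Power, ANCOVA |
|---|---|---|---|---|
| 0.3 | 17.75 | 0.709 | 14.31 | 0.872 |
| 0.5 | 15.00 | 0.844 | 12.99 | 0.927 |
| 0.7 | 11.62 | 0.970 | 10.71 | 0.985 |
| 0.8 | 9.49 | 0.997 | 9.00 | 0.998 |

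**5. Effect of the entry floor of 40.** Assume normal CAPS with mean 60 and SD 20, cut at 40 at week 0. The cut multiplies the baseline SD by 0.794, giving 15.9. Variance of change = 20²(1 − r²) + (1 − r)² × 15.9². The implied SD of change is 22.1/19.1/15.1/12.4 at r = 0.3/0.5/0.7/0.8 (r before the cut), so only r near 0.7 agrees with 15. There the ANCOVA SD is 20 × √(1 − 0.49) = 14.3, and power goes from about 0.84 to about 0.87.

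**6. No gain (k = r).** The SD stays at 15, with 97 df and the factor 1 + 1/96. Power is 0.840 against 0.844.

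**7. Validity.** In 4,000 simulated trials with no effect (r = 0.5, k = 1), both tests rejected in about 4.8% of trials.

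**8. Chance imbalance.** An imbalance of d points shifts the change-score difference by d(1 − r/k). For d = 3 and k = 1 that is 2.1/1.5/0.9/0.6 points at r = 0.3/0.5/0.7/0.8.

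**The case against.** The strongest reply is that nothing is broken. The test holds its error rate, the plan meets its stated power without adjustment, and choosing ANCOVA is good practice rather than a correction. That stands. A reader might infer that the t-test is biased or that the trial is underpowered because of it; the documents support neither.

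The size of the gain is uncertain. Across the scenarios above, the change in power runs from +0.163 (0.709 to 0.872) to −0.004. Section 11.2 attributes the SD of 15 to experience with patients seeking treatment, which could equally describe the spread of scores. On that reading the gain is 0.015 at r = 0.7 and 0.001 at r = 0.8. The table in step 3 also implies a different single-score SD in each row, 15/√(2(1 − r)): from 12.7 at r = 0.3 to 23.7 at r = 0.8. A reader might therefore take 0.956 as the power to expect, or as grounds to cut the sample. The documents do not support that, because they give neither r nor k. The direction of the argument survives; the amount does not become known.

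Replacing only the t-test would leave the Mann-Whitney fallback unadjusted and triggered by the assumptions of a test no longer used. That objection is right, and the fix covers it.

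Finally, section 8.2 records a concurrence dated April 2016 using an abbreviation that section 16.1 uses for continuing review. The study was probably already under way, so the change needs an amendment and not only an edit.

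**Conclusion.** The point holds as a recommended improvement in efficiency. The primary CAPS test is valid but unadjusted, and the covariate that would sharpen it is already scheduled. Under equal SDs with 15 as the SD of change, power would be 0.876 to 0.956 instead of 0.844 for r from 0.8 to 0.3. Once the entry floor is modelled consistently with the assumed mean and SD, the illustration is more modest, about 0.84 to about 0.87. The worst case is a loss of about 0.004. Confidence is high in the direction and low in the amount, which rests on r, k and the meaning of the SD, none of which the documents settle.

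ANCOVA does not resolve the reliance on the last measured value, the missing allowance for dropout after randomisation, or the gap between a response-rate hypothesis and a continuous primary measure.

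**What to change.** 1. In 11.3 and Table 5.7.1, replace the t-test with an ANCOVA of the change already defined (baseline to the final CAPS obtained in Phase II) on treatment and week-0 CAPS, two-sided 0.05.
2. Tie any rank-based fallback to the ANCOVA residuals and adjust it for baseline as well, for example by rank ANCOVA.
3. State that the change score and the covariate use one baseline: the week-0 CAPS, taken before randomisation and the first dose. Align the baseline wording in 9.4 and 11.3 with it.
4. Apply the same adjustment to MADRS, HAM-A, SDS and PCL-C, each with its own week-0 value.
5. Fix the amendment before unblinding.

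Separately, reconcile the visit numbering. Section 9.4 says "the change in CAPS total score will be the primary outcome variable at the end of Phase II (Visit 10"), while the schedule footnote in 9.5 says "Exit visit to be performed at Visit 9 or sooner if the patient is discontinued from the study". Section 9.5 also says patients "must have a Clinician Administered PTSD Scale (CAPS) of 40 at Visits 1 and 2 to be included in the study", but the schedule shows no CAPS at V2, and section 10.2 takes its starting scales from Visit 2. These conflicts exist whichever test is used.

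Cost: an amendment to the wording and one degree of freedom. No new data, no new endpoint and no change in sample size.
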